9.1.2 Sample size/ Justification of Number of Subjects

Based on reported means and standard deviation of PROMS scores of patients undergoing radiation treatment, a total of 60 patients will be required to evaluate a 16% reduction in PROMS score at week 7 (final week) of radiation treatment, with $\alpha = 0.05$ and power = 80%. This assumes a 10% dropout rate.

9.2.1 Secondary Endpoints

9.2.2 Speech and Swallow Function:

Report on change in Speech and swallow performance, as measured by the Performance Status Scale (PSS) for Head and Neck Cancer Patients (see appendix). This will be completed by the treating physician/ speech-language pathologist during the same time points as the primary endpoint.

9.2.3 Weight Loss and Feeding Tube use

Patient weight loss will be evaluated by comparing the percent weight change per patient from baseline to 6 weeks post-treatment between treatment arms using the Wilcoxon-rank sum test at the significance level of 0.05. The feeding tube placement and use will also be documented.

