1.1 INTRODUCTION

1.1.1 Specific Aims

Strategies to minimize and mitigate external beam radiation therapy related mucositis and pain during the treatment of head and neck cancer remain limited. We hypothesize that gabapentin could be used to delay or reduce treatment-related pain, reliance on opioid medication, and improve the quality of life for these patients. The specific aims of this proposed study include the following:

- Evaluate the reduction or delay of mucositis related pain and morbidity with the use of gabapentin in patients with stage III or IV oropharyngeal squamous cell carcinoma undergoing definitive radiation with concurrent chemotherapy as part of their cancer management, compared to standard supportive side effect mitigation – using patient reported quality of life endpoints such as the Patient-Reported Oral Mucositis Symptoms (PROMS) scale.
- Assess morphine-equivalent opioid use in both treatment arms by collecting the patient's narcotic use in the previous 24-hour period at each weekly evaluation during radiation treatment.
- Report on change in Speech and swallow performance, as measured by the Performance Status Scale (PSS) for Head and Neck Cancer Patients.
- Evaluate changes in weight from baseline throughout treatment between the two arms.
- Calculate the proportion of patients who end up requiring a feeding tube by the end of treatment in both arms.
- Evaluate changes in patient-report quality of life using the Functional Assessment of Cancer Therapy Head & Neck (FACT-HN) and PRO-CTCAE metrics.
- Evaluate the adverse events associated with gabapentin.
- Evaluate the severity of radiation mucositis (grade 3-4, CTCAE, v. 4).

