4.3 Protocol Treatment

[figure not shown]

Figure 1: Treatment schema, as described below.

4.3.1 Arm 1

Patients will receive a placebo along the same dosing schedule as the experimental arm (patients randomized to placebo will take the same number of capsules as those assigned to gabapentin).

This will also include standard supportive care for treatment-related pain and mucositis as needed during concurrent chemotherapy and radiation treatment, consisting of the following:

- Viscous lidocaine 2% oral solution
- Oral liquid or solid opioid medications- e.g., morphine, oxycodone. These will be introduced and titrated at the discretion of the treating physician when the patient-reported pain score is ≥ 4 on a 0-10 scale.

4.3.2 Arm 2

Gabapentin will be initiated at a dose of 300 mg to be taken at bedtime of the night prior to the first radiation treatment. During week 1, the dose will be 300 mg three times a day for a total daily dose of 900 mg. Starting week 2, the dose will be 600 mg taken 3 times per day for a total daily dose of 1800 mg. This will continue until one week after the end radiation treatment (week 8). Therapy will then be titrated down to 300 mg three times a day for 1 day, and then discontinued all together. The standard supporting care for treatment-related pain and mucositis described above will also be included.

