4.4 Duration of Follow Up

Patients will be followed for 6 weeks after completion of definitive treatment or until removal (or) termination from study, or until death, whichever occurs first. Patients removed from study for unacceptable adverse events will be followed until resolution or stabilization of the adverse event.

Toxicity notations, quality of life information, and disease status will be recorded. If it is not possible to coordinate a follow-up evaluation at 2 ± 1 months, then a follow-up phone call will

be made to the patient by the treating physician, or clinical trials office designee, in lieu of a visit.

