8. STUDY CALENDAR

The institutional review board (IRB) approval process is expected to be completed by March of 2017. The trial will start accrual of patients subsequently. Given the typical volume of patients treated at our institution, it is expected to take 1-1.5 years to accrue the required 60 patients to complete this study. Patients will be followed up until the first follow-up after completion of radiation treatment (6 weeks). The trial is expected to conclude January of 2019 with data analysis and reporting to take place subsequently.

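### The weight aim is change throughout treatment, but the only planned weight test uses a value taken about 5 weeks after the study drug ends

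*Combined protocol and SAP*

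**What the plan says.** - **Aim (section 1.1.1):** "Evaluate changes in weight from baseline throughout treatment between the two arms".
- **Planned analysis (section 9.2.3):** one comparison between arms, described as "comparing the percent weight change per patient from baseline to 6 weeks post-treatment", "using the Wilcoxon-rank sum test at the significance level of 0.05". Sidedness is not stated.
- **Collection (Table 1):** weight is marked before study therapy, weekly during radiation, and at first follow-up.
- **End of study drug (section 4.3.2):** of the full dose, "This will continue until one week after the end radiation treatment (week 8"). After that, "Therapy will then be titrated down to 300 mg three times a day for 1 day, and then discontinued all together". Under section 4.3.1 placebo follows the same schedule.
- **Follow-up visit (section 8):** "Patients will be followed up until the first follow-up after completion of radiation treatment (6 weeks"). Section 4.4 adds: "If it is not possible to coordinate a follow-up evaluation at 2 ± 1 months, then a follow-up phone call will" take its place.

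No section names an analysis of the weekly weights or says what happens when the 6-week weight is missing.

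**The concern.** The aim and the test address different questions. The aim concerns the period when patients are on study drug and mucositis is developing. The test concerns net weight change to a point some weeks after the drug has stopped, when any effect of treatment is mixed with recovery off drug.

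Three things are at stake. First, a team that follows the plan exactly will report a weight result without having tested its stated aim. Second, if the weekly weights are then analysed because the aim calls for it, the choice of week and method will be made after the data are in. Third, the test relies on one visit that may become a phone call. The plan gives no way to obtain a weight by phone and no rule for a missing value.

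**Working it through.** **No plan figure to reproduce.** The documents give no effect size, SD or power for weight. The 60 patients in section 9.1.2 are for PROMS.

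**Weights used.** Section 4.2.1 gives 35 fractions. At five per week (assumption) that is 35/5 = 7 weeks, in line with section 9.1.2, which calls week 7 the final week. Scheduled weights are 1 baseline + 7 weekly + 1 follow-up = 9. The test uses 2, of which none is on treatment.

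**Time off drug at the tested weight.** I read the 6 weeks as counted from the end of radiation, which section 8, section 9.1.1 and the Table 1 column heading support.
- From the last full-dose day: (42 − 7)/7 = 5.0 weeks.
- From the end of the one-day taper: (42 − 8)/7 = 4.9 weeks.
- If the window of 2 ± 1 months in section 4.4 applies and runs from the end of radiation (assumption), follow-up falls between about day 30.4 and day 91.3. The gap then runs from (30.4 − 8)/7 = 3.2 weeks to (91.3 − 7)/7 = 12.0 weeks.

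**What attenuation could do (illustration only).** Assumptions: 60 less 10% dropout = 54 evaluable, 27 per arm; two-sided 0.05; Wilcoxon efficiency 3/π relative to the t-test under normality.
- Effective n per arm = 27 × 3/π = 25.8.
- Standardised difference detectable with 80% power = (1.960 + 0.842) × √(2/25.8) = 0.78.
- If a fraction f of an on-treatment difference of that size remains at 6 weeks, power ≈ Φ(2.802f − 1.960).

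| Fraction remaining at 6 weeks | Power |
|---|---|
| 100% | 80% |
| 75% | 56% |
| 50% | 29% |
| 25% | 10% |

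The documents do not say which row applies. The table shows only that the result is sensitive to persistence, which the plan does not discuss.

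**The case against.** The strongest defence is that net weight change to 6 weeks after treatment is a coherent secondary endpoint. It carries the cumulative loss over treatment and may matter to patients. That stands, and it is a reason to keep the comparison. It does not make that comparison a test of change throughout treatment.

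Other points on the plan's side limit the criticism:

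- A reader might infer that the weekly weights will be thrown away. The documents do not say so: the weights are collected and the aim to evaluate them remains. What they lack is a named analysis.
- A reader might infer that an on-treatment benefit would be missed. Nothing in the documents shows that a weight difference fades within 5 weeks. "Could be attenuated" is as far as they go.
- A reader might infer substantial loss of patients from the test. Section 4.4 allows the phone call only when no visit can be arranged within a wide window, and no frequency is given. Section 4.5.5 keeps data collected before withdrawal in the analysis, and sections 4.3.4 and 5.1.1 keep patients in intent-to-treat follow-up. Even so, a test that needs the 6-week weight cannot use earlier weights unless a rule says how.
- A reader might infer that averaging the seven weekly weights would bring a clear gain in precision. That needs the same arm effect and variance every week. Section 4.3.2 has a lower dose in week 1, and change from baseline starts at zero. If the arm difference grew linearly to week 7 (assumption), the average would carry (1+2+…+7)/(7×7) = 4/7 of the week-7 effect. With equal between-week correlation ρ, the variance of the average relative to one week is (1 + 6ρ)/7: 0.743 at ρ = 0.7 and 0.914 at ρ = 0.9. Efficiency relative to week 7 alone would be (4/7)²/0.743 = 0.44 and (4/7)²/0.914 = 0.36, a loss.
- A reader might infer that omitting the smoking stratum invalidates the Wilcoxon test. It does not: type I error stays controlled, usually slightly conservatively, and the documents do not show that smoking status predicts weight loss.

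**Conclusion.** The mismatch holds on the documents' own text. The aim is on-treatment weight change. The single named test uses baseline and a weight about 5 weeks after the drug ends, and no on-treatment weight enters any named analysis. This is more than missing detail, because carrying out the plan as written leaves the aim untested.

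The firm figures are 2 of 9 scheduled weights used (assuming five fractions per week) and a gap of 4.9 to 5.0 weeks at the nominal visit. Any loss of power depends on how much of a difference persists to 6 weeks, and any loss of patients depends on how often the visit is missed. The documents supply neither, so no size is claimed for them.

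The point should be fixed, but its reach is limited. Weight is a secondary endpoint, and the PROMS analysis and sample size are untouched.

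**What to change.** In section 9.2.3:

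1. Analyse percent weight change from baseline at weeks 1-7 in a repeated-measures mixed model with arm, week, arm-by-week interaction, baseline weight and smoking stratum. Patients with some weekly weights then contribute even if the 6-week weight is missing.
2. Name the arm difference at week 7 as the single weight contrast. This matches the time point behind the sample size in section 9.1.2 ("a total of 60 patients will be required to evaluate a 16% reduction in PROMS score at week 7 (final week) of radiation treatment"). Do not leave an average over weeks 1-7 as an alternative, because it is a different estimand with different power.
3. Keep percent change to 6 weeks post-treatment with the Wilcoxon test, labelled as a supportive off-drug comparison. Stratifying that test by smoking status is optional.

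The cost is revised analysis wording and a small amount of extra analysis. No new data, visits or patients are needed, and patient management does not change.

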9.2.4 Opioid Use

Patients with at least 1 reported administration of opioid analgesic will be considered to have received opioid analgesics. The total dose of opioid analgesics will be the sum of all opioid analgesic administrations that have been converted to morphine equivalents (see Appendix II). Use of opioid analgesics will be assessed for a 24-hour period before completing the assessment weekly during radiation. The relationship between analgesic use and treatment-related pain will be evaluated using the general linear model with (at minimum) stratification, treatment arm, and compliance.

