2. PATIENT SELECTION

2.1 Conditions for Patient Eligibility:

- 2.1.1 Patients being treated with combination radiation and chemotherapy (definitive) therapy for locally advanced (Stage III and IV) squamous cell carcinoma of the oropharynx.
- 2.1.2 Age ≥ 18 .
- 2.1.3 ECOG performance status 0-1.
- 2.1.4 Patients must provide study specific informed consent prior to study entry and be able to fill out toxicity and quality of life related questionnaires.
- 2.1.5 Patients should be concurrently treated with any of the following chemotherapy regimens: high-dose every three week cisplatin, low dose weekly cisplatin, or weekly carboplatin.

2.2 Conditions for Patient Ineligibility:

- 2.2.1 Patients may not be receiving gabapentin, any other investigational agents, or other anticonvulsants.
- 2.2.2 Patients with metastatic disease are excluded from this clinical trial.
- 2.2.3 Patient with allergies or hypersensitivity to gabapentin.
- 2.2.4 Patients receiving surgery as part of their definitive management.
- 2.2.5 Patients who have received prior chemotherapy or radiation therapy for head and neck cancer.
- 2.2.6 Patients unable to complete the required forms; however, verbal completion is adequate if recorded on the form daily.
- 2.2.7 Uncontrolled serious illness including, but not limited to, ongoing or serious active infection requiring IV antibiotics for over 30 days, symptomatic congestive heart failure, unstable angina pectoris, cardiac arrhythmia other than chronic, stable atrial fibrillation, immunocompromised state, significant hepatic insufficiency, significant hematological disease, and any serious or unstable psychological condition.
- 2.2.8 Patients on any of the following medication that cannot find a suitable substitute during the study period: azelastine, orphenadrine, paraldehyde, thalidomide.
- 2.2.9 Patients with severe renal insufficiency (creatinine clearance of < 60 ml/minute)

2.3 Required laboratory data (to be done at time of enrollement):

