9.2.6 Other Quality of Life Metrics

Patients will be asked to complete the FACT-HN and PRO-CTCAE quality of life forms (see Appendix). The FACT-HN will be assessed at baseline and at the 7-week (final week) of radiation. The PRO-CTCAE will be assessed at baseline and weekly with the PROMS scale.

The change in scores from baseline to the 6-week follow-up timepoint will be used for analysis.

All assessments are summarized in Table 1.

Table 1. Subject assessments.

| Parameters | Prior to Study Therapy | Weekly During Radiation Therapy | At First Follow-up (6-weeks post completion) |
|---|------------------------|---------------------------------|--|
| History and Physical ^a | X | | X |
| Performance status ^a | X | | X |
| Creatinine | X | | |
| PROMS Score ^b | X | X | X |
| HN-PSS Score ^a | X | X | X |
| FACT H&N ^b | X | | X |
| Weight | X | X | X |
| Daily opioid use (in morphine equivalents) ^a | X | X | X |
| Assess if feeding tube has been placed ^a | X | X | X |
| CTCAE and other adverse events ^a | X | X | X |
| PRO-CTCAE questionnaire ^b | X | X | X |

^a Physician or evaluator reported.

^b Patient reported.

REFERENCES

1. Starmer, H.M., et al., *Effect of gabapentin on swallowing during and after chemoradiation for oropharyngeal squamous cell cancer*. Dysphagia, 2014. **29**(3): p. 396-402.
2. Chaturvedi, A.K., et al., *Human papillomavirus and rising oropharyngeal cancer incidence in the United States*. Journal of Clinical Oncology, 2011. **29**(32): p. 4294-4301.
3. Marur, S. and A.A. Forastiere, *Head and neck cancer: changing epidemiology, diagnosis, and treatment*. Mayo Clin Proc, 2008. **83**(4): p. 489-501.
4. Pignon, J.-P., et al., *Meta-analysis of chemotherapy in head and neck cancer (MACH-NC): an update on 93 randomised trials and 17,346 patients*. Radiotherapy and Oncology, 2009. **92**(1): p. 4-14.
5. Trott, A., et al., *TAME: development of a new method for summarising adverse events of cancer treatment by the Radiation Therapy Oncology Group*. Lancet Oncol, 2007. **8**(7): p. 613-24.
6. Moslemi, D., et al., *Management of chemo/radiation-induced oral mucositis in patients with head and neck cancer: A review of the current literature*. Radiother Oncol, 2016. **120**(1): p. 13-20.

7. Epstein, J.B., et al., *Neuropathic and nociceptive pain in head and neck cancer patients receiving radiation therapy*. Head & neck oncology, 2009. **1**(1): p. 1.

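### Section 9.2.4 does not prespecify adjustment for baseline opioid dose, although opioid users may enter the trial and Table 1 collects it

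*Combined protocol and SAP*

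**What the plan says.** Four places in the combined protocol and SAP bear on this.

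- **Eligibility (section 2.2).** The drug-related exclusions are "Patients may not be receiving gabapentin, any other investigational agents, or other anticonvulsants" and, separately, "Patients on any of the following medication that cannot find a suitable substitute during the study period: azelastine, orphenadrine, paraldehyde, thalidomide". Opioids appear in neither, and section 2.1 does not require patients to be opioid-free.
- **Endpoint (section 9.2.4).** "Patients with at least 1 reported administration of opioid analgesic will be considered to have received opioid analgesics". For dose, "The total dose of opioid analgesics will be the sum of all opioid analgesic administrations that have been converted to morphine equivalents". Nothing separates new from continuing use, and no baseline dose is subtracted. On timing, "Use of opioid analgesics will be assessed for a 24-hour period before completing the assessment weekly during radiation".
- **Model (section 9.2.4).** The relationship between analgesic use and treatment-related pain is to be examined with "the general linear model with (at minimum) stratification, treatment arm, and compliance". Baseline opioid use is not named. The only stratification factor is smoking (section 4.5.1).
- **Data collection (Table 1, section 9.2.6).** The row beginning "Daily opioid use (in morphine equivalents" is marked before study therapy, weekly during radiation and at first follow-up. The pre-therapy value exists, but no section gives it a role. By contrast, section 9.2.3 analyses weight as change from baseline, and section 9.2.6 does the same for the other quality-of-life scores.

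**The concern.** Less reliance on opioids is part of the trial's hypothesis, and morphine-equivalent use in both arms is a specific aim (section 1.1.1). Patients with oropharyngeal cancer may already take opioids when they enrol, and this plan admits them. Their dose at entry may predict their dose during radiation. A model without that baseline leaves predictable variation in the error term and does nothing about a chance difference between small arms. For a yes/no measure, a patient who enters on opioids and stays on them is a user in either arm and carries no information about the drug.

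At stake is the precision and readability of a secondary comparison that no power statement supports.

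**Working it through.** **Inputs from the documents.** N = 60 with 10% dropout (section 9.1.2); 1:1 allocation (section 4.5.1). So there are 30 per arm randomised and 60 × 0.90 = 54 evaluable, or 27 per arm. The 60 is justified for PROMS at week 7 only, and cannot be reproduced because the mean and SD behind it are not given. There is no stated figure for opioid use to reproduce.

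**Assumed inputs (the documents give none).** Share on opioids at entry, b: 10% to 30%. Correlation of on-treatment dose with baseline dose, ρ: 0.3 to 0.6. Two-sided 5% test. Opioid-use rates as shown below.

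**1. Precision, if opioid dose is the outcome.** Adjusting for baseline multiplies residual variance by 1 − ρ². With 27 per arm, the standard error in SD units is √(2/27 × (1 − ρ²)). The difference detectable with 80% power is (1.96 + 0.84) times that. Power at a standardised difference of 0.5 is Φ(0.5/SE − 1.96).

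| ρ | 1 − ρ² | Variance removed | Detectable difference | Power at 0.5 |
|---|---|---|---|---|
| 0 (unadjusted) | 1.00 | 0% | 0.76 | 45% |
| 0.3 | 0.91 | 9% | 0.73 | 49% |
| 0.5 | 0.75 | 25% | 0.66 | 56% |
| 0.6 | 0.64 | 36% | 0.61 | 63% |

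**2. Chance imbalance.** Let X and Y be the numbers of opioid users at entry in two arms of 30, each Binomial(30, b).

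| b | P(arms differ by 4 or more) | SD of difference in shares, √(2b(1 − b)/30) |
|---|---|---|
| 10% | 0.128 | 7.7 points |
| 20% | 0.256 | 10.3 points |
| 30% | 0.323 | 11.8 points |

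**3. Dilution of a yes/no comparison.** If every user at entry is still taking opioids at some weekly visit, the observed proportion in an arm is b + (1 − b)p, where p is the rate among patients opioid-free at entry. The difference between arms is then (1 − b) times the difference in p. A 20-point difference becomes 20 × 0.9 = 18, 20 × 0.8 = 16 or 20 × 0.7 = 14 points. If some stop before the first weekly assessment, the shrinkage is smaller.

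**4. Would restricting to opioid-free patients recover power?** Restriction restores the difference but leaves only 27(1 − b) per arm. Power is by the normal approximation for two proportions (pooled variance under the null).

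| Rates among opioid-free | b | All patients, 27 per arm | Opioid-free only |
|---|---|---|---|
| 90% v 70% | 10% | 40% | 41% |
| 90% v 70% | 20% | 36% | 37% |
| 90% v 70% | 30% | 31% | 33% |
| 90% v 60% | 20% | 60% | 63% |

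The gain is one to three percentage points, because the lost patients offset most of the larger difference.

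**The case against.** The case on the other side is strong, and much of it stands.

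- **The covariate list is open.** The bracketed words in "evaluated using the general linear model with (at minimum) stratification, treatment arm, and compliance" set a floor, so adding baseline dose is already permitted. This stands: the gap is one of prespecification. It still matters, because choosing a covariate after seeing the data is what a plan should prevent.
- **Randomisation protects the comparison.** This stands. An unadjusted comparison is unbiased on average, and its standard error already reflects variation in baseline use. Adjustment buys precision and removes a chance difference; it does not repair a bias.
- **The arm comparison is itself barely written.** The model is worded as analgesic use against pain, and the outcome is not identified. No between-arm test of any-use is stated, whereas sections 9.2.3 and 9.2.5 name theirs. This stands, and it limits the arithmetic: step 1 applies only if opioid dose is the outcome, and step 3 only if a yes/no comparison is made.
- **The sizes are all conditional.** This stands. If few patients enter on opioids, the effect is close to nil.

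A reader might infer that anyone on opioids before the first capsule counts as a user whatever happens later. Section 9.2.4 does not support that: it places the assessment in the weekly visits during radiation, so such a patient counts only if still taking opioids then.

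**Conclusion.** The point holds as a missed, cost-free improvement to a secondary analysis. The plan admits opioid users and collects their baseline dose, but does not commit to using it. Given opioid dose as the outcome and ρ of 0.3 to 0.6, adjustment would remove 9% to 36% of residual variance. Given 10% to 30% of patients on opioids at entry, two arms of 30 differ by four or more such patients with probability 13% to 32%, with no prespecified correction. The yes/no difference shrinks at most by the factor (1 − b).

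Two stronger conclusions are not supported. A reader might infer that the opioid comparison is biased; random allocation rules that out on average. A reader might also infer that the any-use measure should be replaced by new use among opioid-free patients. That would drop randomised patients for almost no power, and would sit badly with the intent-to-treat follow-up in sections 4.3.4 and 5.1.1. The primary PROMS analysis is untouched.

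**What to change.** In section 9.2.4:

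1. State the between-arm model explicitly, with on-treatment morphine-equivalent opioid dose as the outcome and arm as the term of interest, and say how the weekly values enter it.
2. Prespecify baseline 24-hour morphine-equivalent dose, from the pre-therapy column of Table 1, as a covariate.
3. Keep any opioid use during radiation as a measure in all randomised patients.
4. Report new use among patients opioid-free at baseline as a supplementary analysis only, with the number of patients on opioids at entry shown by arm.

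The cost is a few sentences of analysis text, settled before unblinding, and one model degree of freedom. Eligibility, treatment, data collection and sample size do not change.

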APPENDIX III

Weekly Patient and Clinician Reported Questionnaires

Patient Reported Oral Mucositis Symptom (PROMS) Scale

1. Mouth* pain - *Mouth encompass also lips, cheeks, tongue, gums, palate and throat
no pain _____ worst possible pain

2. Difficulty speaking because of mouth* sores
no trouble speaking _____ impossible to speak

3. Restriction of speech because of mouth* sores
no restriction of speech _____ complete restriction of speech

4. Difficulty eating hard foods (hard bread, potato chips etc) because of mouth* sores
no trouble eating hard foods _____ impossible to eat hard foods

5. Difficulty eating soft foods (Jello, pudding etc) because of mouth* sores
no trouble eating soft foods _____ impossible to eat soft foods

6. Restriction of eating because of mouth* sores
no restriction of eating _____ complete restriction of eating

7. Difficulty drinking because of mouth* sores
no trouble drinking _____ impossible to drink

8. Restriction of drinking because of mouth* sores
no restriction of drinking _____ complete restriction of drinking

9. Difficulty swallowing because of mouth* sores
not difficult to swallow _____ impossible to swallow

10. Change in taste
no change in taste _____ complete change in taste

I have taken pain medication today.

Yes

No

The name of your pain medication: _____

What is the dose you are taking? _____

How do you take your pain medication? (for example, by mouth, by patch, by injection) _____

How often do you take your pain medication? (for example, once a day, twice a day)

**PERFORMANCE STATUS SCALE FOR
HEAD AND NECK CANCER PATIENTS: PSS-HN**

Patient Name _____ ID# /____/____/____/____/____/ Date /____/____/____/____/

NORMALCY OF DIET /____/

- | | |
|-----|--|
| 100 | Full diet (no restrictions) |
| 90 | Full diet (liquid assist) |
| 80 | All meat |
| 70 | Raw carrots, celery |
| 60 | Dry bread and crackers |
| 50 | Soft chewable foods (e.g., macaroni, canned/soft fruits, cooked vegetables, fish, hamburger, small pieces of meat) |
| 40 | Soft foods requiring no chewing (e.g., mashed potatoes, apple sauce, pudding) |
| 30 | Pureed foods (in blender) |
| 20 | Warm liquids |
| 10 | Cold liquids |
| 0 | Non-oral feeding (tube fed) |

PUBLIC EATING /____/

- | | |
|-----|---|
| 100 | No restriction of place, food or companion (eats out at any opportunity) |
| 75 | No restriction of place, but restricts diet when in public (eats anywhere, but may limit intake to less "messy" foods (e.g., liquids) |

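### Section 9.2.4 identifies opioid users from weekly 24-hour look-backs, so sparse users can be missed and onset of opioid use is dated late and not analysed

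*Combined protocol and SAP*

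**What the plan says.** Section 9.2.4 (Opioid Use) does three things. It defines a user: "Patients with at least 1 reported administration of opioid analgesic will be considered to have received opioid analgesics". It defines a dose: "The total dose of opioid analgesics will be the sum of all opioid analgesic administrations that have been converted to morphine equivalents". It then sets the window: "Use of opioid analgesics will be assessed for a 24-hour period before completing the assessment weekly during radiation". The Specific Aims (1.1.1) use the same window, collecting "narcotic use in the previous 24-hour period at each weekly evaluation during radiation treatment".

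Table 1 (in 9.2.6) lists the variable as "Daily opioid use (in morphine equivalents") and schedules it before study therapy, weekly during radiation and at the 6-week follow-up, reported by the physician or evaluator.

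The medication items printed after the PROMS questions in Appendix III open with "I have taken pain medication today". They go on to ask for the drug name, dose, route and usual frequency. They cover any pain medication, and none asks when it was started.

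The hypothesis in 1.1.1 reads in part: "We hypothesize that gabapentin could be used to delay or reduce treatment-related pain, reliance on opioid medication". The rationale in 1.2.3 again pairs delaying or reducing with pain and opioid reliance. No diary, question covering the interval between visits, first-opioid date or time-to-first-opioid analysis appears in 9.2.4, Table 1 or Appendix III.

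**The concern.** Ever-use is a statement about the whole treatment period, but it is read from one day in seven. Section 4.3.1 makes opioids an as-needed part of supportive care, so early use may be intermittent. A patient who takes an opioid only on days outside the windows is classed as never having received one.

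Onset has the same weakness. If gabapentin postpones the need for opioids, the effect should show as a later first dose. The plan can offer only the visit at which use was first caught, and it specifies no comparison of onset. What is at stake is the reliability of the ever-use classification and the precision of any statement about delay. Days that were not asked about cannot be recovered reliably after the trial.

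**Working it through.** The plan states no figure for the opioid endpoint, so there is nothing to reproduce. The check asks how often the specified windows would miss a true user.

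**Inputs from the documents.** One 24-hour window per weekly visit (9.2.4, 1.1.1). Week 7 is the final week of radiation (9.1.2), which gives 7 windows. 60 patients, 10% dropout (9.1.2), 1:1 allocation (4.5.1).

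**Assumptions.** Opioid use falls on *k* random days a week for *w* weeks, unrelated to visit days. The documents give no use pattern, so *k* and *w* are varied.

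**Step 1, coverage.** 7 windows / 49 days = 1/7, about 14% of radiation days.

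**Step 2, chance that a user is never recorded.** Each window misses with probability 1 − k/7, so over *w* weeks the probability is (1 − k/7)^w.

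| Days of use per week | 1 week of use | 3 weeks | 7 weeks |
|---|---|---|---|
| 1 | 6/7 = 86% | (6/7)^3 = 63% | (6/7)^7 = 34% |
| 2 | 5/7 = 71% | (5/7)^3 = 36% | (5/7)^7 = 9.5% |
| 3 | 4/7 = 57% | (4/7)^3 = 19% | (4/7)^7 = 2% |
| 7 (daily) | 0% | 0% | 0% |

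**Step 3, delay in dating onset.** Simulation with first use on a random day in weeks 3 to 4, each later day a use day with probability k/7, and the window on the last day of each week. Lag is counted among patients who are detected.

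| Days of use per week | Mean lag to first positive report | Never detected |
|---|---|---|
| daily | 3.0 days | 0% |
| 2 | 9.9 days | 19% |
| 1 | 10.6 days | 43% |

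**Step 4, equal misses in both arms.** 60 × 0.9 = 54 evaluable, 27 per arm. Take true ever-use of 90% and 60% (assumed), and a two-sided 0.05 test of two proportions by the normal approximation. If a share *m* is missed in each arm, the observed rates are 0.9(1 − m) and 0.6(1 − m). Power is 73% at m = 0, 57% at 10%, 43% at 20% and 30% at 34%. The plan specifies no such test; the figures only show what equal misses would cost.

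**Step 5, unequal misses.** Suppose true ever-use is 90% in both arms. Control users take opioids daily (0% missed) and gabapentin users on 2 days a week for 7 weeks (9.5% missed). Observed ever-use is 90% against 0.9 × (1 − 0.095) = 81%, an apparent gap of about 9 percentage points where ever-use does not differ.

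**The case against.** The case for leaving the plan alone has weight.

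- A reader might infer that intermittent users as a group are counted as opioid-free. They are not: one positive window is enough, and the 7-week column above falls to 2% at 3 days a week. A patient who progresses to sustained daily use is caught. Section 4.2.10 expects severe mucositis or dysphagia in about two thirds of patients, so the documents do not suggest that use which stays sparse is typical.
- A reader might infer that delay cannot be measured. It can, as the interval in which use was first reported, with about 3 days' lag for daily users. What stands is that this date runs late for intermittent users and that no analysis uses it.
- A reader might infer that misses always dilute the treatment difference. That requires equal misses; sparser use under gabapentin would push the other way.
- A reader might see a contradiction between the 24-hour window and the wording "I have taken pain medication today". That item covers all pain medication, Table 1 assigns the opioid variable to the physician or evaluator, and 9.2.4 does not name the form as its source. The mismatch matters only if the form feeds the endpoint. Its frequency question may also reveal some non-daily use, although 9.2.4 makes no use of it.
- A reader might say the defined total dose is unobtainable. Read with the sentence after it and with Table 1's label, the sum can mean drugs and doses within the 24-hour window. This is loose wording rather than an error.
- The 24-hour recall matches the stated opioid aim and favours accurate doses. The only opioid model in 9.2.4 relates analgesic use to pain, with arm as a term, and no between-arm test of ever-use is planned. The hypothesis sentence can also be read as attaching delay to pain alone.

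These points limit the concern but do not remove it. Ever-use is still defined, is still read from about one day in seven, and no start date is collected.

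**Conclusion.** The point holds in limited form. The weekly 24-hour window suits a daily dose but is weak for classifying ever-use and for dating onset. How many patients would be missed depends on a use pattern the documents do not give. Under random-day use it ranges from none, for daily users, to 34% for use on 1 day a week throughout radiation, and higher for short spells. The direction of bias is not fixed: equal misses cost power, and unequal misses could exaggerate the benefit of gabapentin. Delayed opioid reliance is a fair but not the only reading of the hypothesis. Because opioid use is a secondary endpoint, this is a moderate, inexpensive improvement. It does not affect the primary PROMS analysis.

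**What to change.** In 9.2.4 and Table 1:

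1. Define having received opioids as any opioid taken since the previous visit, asked at each weekly visit and at the 6-week visit.
2. Record the date of the first opioid dose and compare time to first opioid by arm. Say how patients already on opioids at baseline are handled (Table 1 identifies them). If only the interval between visits is known, use a method for interval-censored data.
3. Keep the 24-hour morphine-equivalent value and describe it as the daily dose at each assessment, in line with Table 1.
4. State whether the Appendix III medication item is a source for this endpoint. If it is, align its recall period with the 24-hour window. The item stands outside the ten PROMS questions, so the scale is untouched.

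The cost is two short questions at visits that already take place, plus a few sentences of text. The downside is that a yes/no recall over 7 days is less exact than a 24-hour dose recall, and the interval before the follow-up visit is about six weeks. The longer recall should therefore serve only for any use and the first date, not for dose.
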